## 9.5 Mucosal secretion sampling

Mucosal secretion samples will be collected at baseline (prior to the first vaccination) and at other timepoints indicated in Appendix F and Appendix G. Participants who have consented to any or all mucosal sampling procedures (Appendix A), and who meet the screening criteria for these procedures, will provide samples of rectal fluids, semen (participants born male only), and/or cervicovaginal secretions (participants born female only).

- Participants who consent to provide optional cervicovaginal, rectal, or semen secretions will be tested for the following infections at the mucosal sampling visits: gonorrhea, chlamydia, and syphilis. Participants who were born female who consent to provide cervicovaginal samples will be tested for trichomoniasis and bacterial vaginosis and may be tested for hyphae/budding yeast (if clinically indicated). Test results will be provided to participants and all participants who test positive for 1 or more of these infections will receive counseling as well as treatment or referral for treatment as appropriate. Sample collection will not be performed or may be deferred to a later date within the visit window if a contraindication to sampling (eg, active genital tract infection [GTI]) is present (as indicated below).
- Rectal fluid sampling (optional, both sexes). For participants born female, a pregnancy test must be performed and be negative prior to any rectal mucosal

sampling. Participants should abstain from receptive anal sex, insertion of any foreign object or substance into the anus (including but not limited to cleaning products [creams, gels, lotions, pads, etc.], lubricant, enemas, and douching even with water), and using perianal or intra-anal steroid or other anti-inflammatory cream in or around the anus for 48 hours prior to sample collection. Rectal secretion sampling should be deferred if a participant is menstruating, but should be performed as soon as possible, within the visit window. In addition, rectal sampling will not be performed (or may be deferred to a later date within the visit window) if there is a contraindication to rectal secretion sampling, such as an active infection or inflammation of the colorectal area (such as an HSV-2 outbreak or inflamed hemorrhoids or colitis/diarrhea) or if the participant has any active GTI.

- Cervicovaginal secretion sampling (optional, only for participants who were born female). Participants who are age 21 or older must report having had a Pap smear within the 5 years prior to enrollment, with the latest result reported as normal or ASCUS (atypical squamous cells of undetermined significance) with no evidence of high-risk HPV; if high-risk HPV testing was not conducted, the participant must report having had a Pap smear within the 3 years prior to enrollment, with the latest result reported as normal or ASCUS. For participants capable of becoming pregnant, a pregnancy test must be performed and must be negative prior to any cervicovaginal mucosal sampling. Cervicovaginal mucosal sampling should be deferred if a participant is menstruating, but should be performed as soon as possible, within the visit window. In addition, cervicovaginal sampling will not be performed (or may be deferred to a later date within the visit window) if a participant has an active ulcerative genital lesion or is known to have an active GTI at the scheduled timepoint. Participants providing cervico+vaginal secretion samples should be advised as follows:
  - Do not use anything with spermicide, lubricants, or topical/intravaginal medications (eg, topical yeast infection treatments) for 48 hours before the samples are collected;
  - Do not douche for 48 hours before the samples are collected;
  - Do not have vaginal sex or insert any foreign object or substance into the vagina for 48 hours before the samples are collected;
- Semen sampling (optional, only for participants who were born male). Participants providing semen samples are asked to refrain from ejaculation, using anything with lubricants, putting saliva on the penis, or having oral sex for at least 48 hours prior to specimen collection. In addition, semen sampling will not be performed (or may be deferred to a later date within the visit window) if a participant is known to have an active GTI at the scheduled timepoint.

## 9.6 Annual health contact

Participants will be contacted at 2 years following initial study injection (Appendix H). At this contact, CRS staff will collect the information listed below. Clinic visits will only be required if HIV confirmatory testing is necessary (Section 9.7.1); however, a clinic visit may be arranged for other reasons.

- Confirmation of vital status; if deceased, attempt to learn cause and date of death;

- If participant is alive, record the participant's responses to questions regarding any occurrence of the following events since the last HVTN study contact:
  - Life-threatening adverse experiences;
  - Persistent or significant disability/incapacity;
  - Hospitalizations and reasons;
  - Other important medical events that may jeopardize the participant or may require intervention to prevent 1 of the other outcomes listed above;
  - New chronic conditions requiring more than 30 days of medical intervention or medication;
  - New diagnosis of HIV infection; and
  - Pregnancies and outcomes, including congenital anomalies/birth defects.

All such events will be recorded, and adverse events will be assessed for relationship to study product(s).

#### **9.6.1 Interim contacts**

CRSs may report safety information obtained at a contact other than the annual contact. These contacts are reported as interim visits.

### **9.7 HIV counseling and testing**

HIV counseling will be performed in compliance with the CDC's guidelines or other local guidelines for HIV counseling and referral. HIV testing will be performed in accordance with the current HVTN HIV testing algorithm following enrollment.

Participants will be counseled routinely during the trial on the avoidance of HIV infection and on the potential negative social impacts of testing Ab positive due to the vaccine. They will also be counseled on the risks of HIV Ab testing outside of the HVTN CRSs and will be discouraged from doing so during study participation and/or during any period of vaccine-induced positive serology.

Study staff will take particular care to inform study participants of the likelihood of routine HIV testing being offered or performed outside the study CRS at emergency rooms, clinics, and medical offices. Such testing has become more likely due to the CDC's revised guidelines for HIV counseling and testing, as well as policy changes in many countries to make HIV testing more frequent and routine. CRS staff should inform participants of their right to opt out of HIV testing outside the study site. CRS staff should inform study participants if local and/or state policies and regulations permit medical providers to perform HIV testing without first informing patients. If this is the case, then CRS staff should advise study participants that they may decline testing preemptively. CRS staff should also inform participants if positive results must be reported to local public health authorities. CRS staff should also inform participants of the need to maintain study blinding by getting HIV testing only at the study CRS. CRS staff should provide participants with CRS contact information and should encourage participants to ask medical providers to contact the CRS. The CRS can verify that the participant is in an HIV vaccine clinical trial and should only be tested at the study CRS.

Potential participants identified as being HIV infected during screening are not enrolled. All participants who become HIV infected during the study will be terminated from this study. Potential and enrolled participants identified as HIV infected will be referred for medical treatment, counseling, and management of the HIV infection. These individuals may also be referred to appropriate ongoing clinical trials or observational studies.

### 9.7.1 Distinguishing intercurrent HIV infection from vaccine-induced positive serology

The study product may elicit an Ab response to HIV proteins. Therefore, vaccine-induced positive serology may occur in this study. Several precautionary measures will be taken to distinguish intercurrent HIV infection from vaccine-induced positive serology. These precautionary measures include:

- Participants will have physical examinations at visits specified in Appendix G. Signs or symptoms of an acute HIV infection syndrome, an intercurrent illness consistent with HIV-1 infection, or probable HIV exposure would prompt a diagnostic workup per the HVTN algorithm for Recent Exposure/Acute Infection Testing to determine HIV infection.
- HIV testing will be performed at multiple timepoints throughout the study (Appendix G). The Laboratory Program (or approved diagnostic laboratory) will follow the HVTN HIV testing algorithm (as described in the HVTN Laboratory Manual of Operations), which is able to distinguish vaccine-induced Ab responses from actual HIV infections.
- All participants can receive HIV-1 diagnostic testing from the site following their last scheduled visit until they are told that they did not receive an HIV vaccine or that they do not have vaccine-induced seropositivity.
- All participants who received vaccine product and who have vaccine-induced positive or indeterminate HIV-1 serology (as measured by the standard anti-HIV Ab screening tests) at or after the study is unblinded will be offered poststudy HIV-1 diagnostic testing (per the HVTN poststudy HIV-1 testing algorithm) periodically and free of charge as medically/socially indicated (approximately every 6 months) unless or until HIV Ab testing is no longer the standard test in clinical settings.

### 9.7.2 VISP registry

Experimental HIV vaccines may induce Ab production to HIV antigens, producing reactive results on commercially available HIV test kits. This is called “vaccine-induced seropositivity” (VISP) (Section 9.7.1). In order to provide poststudy HIV testing to distinguish between VISP and HIV infection, and to mitigate potential social harms resulting from VISP in HIV vaccine recipients who are not infected with HIV, the HVTN has created a VISP registry. Following study unblinding, the registry will allow trained staff to verify that an individual has received an HIV vaccine, and therefore has the potential for VISP. Information in the VISP registry will not be used for research. Rather, the registry exists to support provision of poststudy testing and counseling services to HIV vaccine recipients. The registry contains the names of all study participants, unless they request that their names be removed.

## 9.8 Contraception status

Contraception status is assessed and documented at every scheduled clinic visit for a participant who was born female and who is sexually active in a way that could cause that participant to become pregnant. Prior to enrollment and throughout the study, staff will ask participants to verbally confirm their use of adequate contraceptive methods. A participant who was born female and is sexually active in a way that could cause that participant to become pregnant should be reminded at all scheduled clinic visits of the importance of using contraception and should be referred to specific counseling, information, and advice as needed. (Specific contraception requirements are listed in Section 7.1). This reminder should be documented in the participant's study record.

Self-reported infertility—including having reached menopause (no menses for 1 year) or having undergone hysterectomy, bilateral oophorectomy, or tubal ligation—must be documented in the participant's study record.

## 9.9 Urinalysis

Dipstick testing may be performed in the clinic or the lab, as long as the required elements (glucose, protein, and hemoglobin) are tested. The examination is performed on urine obtained by clean catch.

If the screening dipstick is transiently abnormal due to menses or infection, document this issue in the participant's source documentation. For infection, provide appropriate treatment and/or referral. Following resolution, repeat the dipstick and, if within the eligibility limits specified in the protocol, the participant may be enrolled.

Follow-up urinalysis should be deferred if a participant is menstruating, but should be performed as soon as possible. If a follow-up dipstick is abnormal due to a participant's menstrual period, document in the comment section of the case report form (CRF) and repeat the dipstick once the participant is no longer menstruating. A micro-urinalysis is not required.

## 9.10 Assessments of reactogenicity

For all participants, baseline assessments are performed before and reactogenicity assessments are performed after each vaccination. All reactogenicity symptoms are graded according to the Division of AIDS Table for Grading the Severity of Adult and Pediatric Adverse Events (DAIDS AE Grading Table), Version 2.0 [November 2014], except as noted in Section 11.2.2).

The reactogenicity assessment period is 3 full days following each vaccination per the assessment schedule shown in Table 9-1. Participants are instructed to record symptoms using a postvaccination symptom log and to contact the site daily during the assessment period. Clinic staff will follow new or unresolved reactogenicity symptoms present at day 3 to resolution. Participants are instructed to contact the clinic for events that arise during the period between vaccination and the next scheduled visit. In general, a participant who self-reports any postvaccination reaction greater than mild is seen by a clinician within 48 hours after onset, unless the reaction is improving and/or has completely resolved.

Reactogenicity events are reported using CRFs that correspond to the time of assessment in Table 9-1. Reactogenicity assessments include assessments of systemic and local symptoms, vaccine-related lesions, and lymph nodes. Events not listed on a CRF, or with an onset after the reactogenicity assessment period (day of vaccination and 3 full days after), or those meeting SAE/adverse events requiring expedited reporting to DAIDS criteria, are recorded on an adverse experience log form.

**Table 9-1 Schedule of reactogenicity assessments**

| Day            | Time                                       | Performed by                  |
|----------------|--|-------------------------------|
| 0 a | Baseline: before vaccination               | HVTN CRS staff                |
|                | Early: 25-60 minutes after vaccination     | HVTN CRS staff                |
|                | Between early assessment and 11:59pm day 0 | HVTN CRS staff or participant |
| 1              | Between 12:00am and 11:59pm day 1          | HVTN CRS staff or participant |
| 2              | Between 12:00am and 11:59pm day 2          | HVTN CRS staff or participant |
| 3 b | Between 12:00am and 11:59pm day 3          | HVTN CRS staff or participant |

a Day of vaccination

b New or unresolved reactogenicity symptoms present on day 3 are followed until resolution

### 9.10.1 Assessment of systemic and local symptoms

Systemic symptoms include increased body temperature, malaise and/or fatigue, myalgia, headache, chills, arthralgia, nausea, and vomiting. Local symptoms include pain and/or tenderness proximal to the injection site. The daily maximum severity reached for each symptom during the assessment period is reported.

Body temperature is measured by oral or infrared thermometry and reported in degrees Celsius. If temperature is measured in Fahrenheit, the conversion to Celsius should be documented in the participant's chart note. A measurement is taken once daily during the assessment period and should be repeated if participant is feeling feverish.

### 9.10.2 Assessment of injection site

Typical injection site reactions are erythema/induration/swelling. The maximum horizontal and maximum vertical measurements for all injection site reactions are recorded.

All injection site reactions are monitored until resolution. Areas of erythema/induration/swelling 25 cm^2 or more are followed daily; otherwise, the frequency of follow-up is based on clinician judgment.

### 9.10.3 Assessment of lymph nodes

This assessment is required only when reactogenicity assessments are performed by HVTN CRS staff, not by the participant.

Only the proximally draining lymph nodes are assessed (eg, axillary nodes on the same side of the body for injections given in the deltoid). Lymph nodes are first evaluated for enlargement and tenderness. If they are found to be enlarged, measurements are taken to determine the size (widest diameter) of the enlarged node(s).

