##### 4.8.1.1 Clinical safety experience

In HVTN 065 and HVTN 094, there were no reports of severe local (injection site) reactogenicity. In HVTN 205, 2 participants (1 DDMM, 1 MMM) experienced severe pain and/or tenderness at the injection site, and 4 participants (3 DDMM, 1 MMM) experienced severe systemic reactogenicity symptoms such as malaise and/or fatigue, chills, or fever. In HVTN 094, two participants reported severe malaise and/or fatigue and one participant reported severe headache.

One participant in HVTN 065 developed chest tightness and dyspnea 30 min after vaccination with MVA/HIV62B, which was considered a possible allergic reaction, probably related to vaccination. In HVTN 205, 1 participant experienced an allergic reaction  $\leq 15$  minutes after the second MVA/HIV62B vaccination, which was considered definitely related to the vaccine. The symptoms resolved within 2 hours.

One individual in HVTN 065 experienced a moderate decrease in neutrophils 14 days following the first DNA vaccination. One person in HVTN 094 experienced a mild decrease in neutrophils 3 days after the first GEO-D03 vaccination. One person in HVTN 205 experienced a severe decrease in lymphocyte count 1 day after receiving MVA/HIV62B. Other AEs related to vaccination were such injection site symptoms such as pain, pruritus, swelling, induration, hematoma/bruise or paresthesia; axillary lymphadenopathy or axillary tenderness, dizziness or lightheadedness, nasal congestion, tremor and dyspnea. All of these AEs resolved without complications. In this study, participants will have already received 2 or 3 injections of MVA/HIV62B previously in HVTN 205.

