**Table 4-6 Summary of potential risks of study products and administration**

|                   |   |
|-------------------|---|
| Common            | 
 
• Mild to moderate injection site pain, tenderness, erythema, or swelling/induration/edema
 
• Malaise/fatigue, myalgia, or headache in the first few days following injection
 
• A vaccine-induced positive HIV Ab test result
 
• Axillary lymph node swelling, pain, or tenderness
 
   |
| Less common       | 
 
• Severe injection site pain or tenderness
 
• Fever, chills, flu-like syndrome, arthralgia, rash, nausea, vomiting, or dizziness in the first few days following injection
 
• Vasovagal reaction/lightheadedness/dizziness related to the injection procedure/tremor
 
• Transient changes in clinical laboratory values
 
• Injection site hematoma, bruising/ecchymosis, other transient lesions, itching, or bleeding related to the injection procedure
 
 |
| Uncommon or rare  | 
 
• Severe localized injection site reaction, such as sterile abscess or secondary bacterial infection
 
• Allergic reaction, including rash, urticaria, angioedema, bronchospasm, or anaphylaxis
 
• Muscle damage at the injection site
 
   |
| Unknown frequency | 
 
• Myo/pericarditis
 
  |
| Theoretical risks | 
 
• Autoimmune disease
 
• Effects on a participant's response to an approved HIV vaccine administered in the future
 
• Effects on susceptibility to HIV, if the participant is exposed to HIV
 
• Effects on the course of HIV infection/disease, if the participant is infected with HIV
 
• Effects on the fetus and on pregnancy
 
   |

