### 9.3 Enrollment and vaccination visits

Enrollment is simultaneous with first vaccination. The time interval between randomization and enrollment should not exceed 4 working days. The HVTN CRS registers the participant by scheduling the day 0 visit (enrollment) via the Web-based randomization system, and requests the randomization assignment. Circumstances may require a participant's enrollment visit to be changed. This may exceed the 4-day randomization time limit.

At all vaccination visits, the following procedures are performed before vaccination:

- Abbreviated physical examination, including weight, vital signs, and a symptom-directed evaluation by history and/or appropriate physical exam based on participant self-reported symptoms or complaints;
- Assessment of baseline reactogenicity parameters;
- Assessment of concomitant medications (as described in Section 9.2);
- Cardiac symptom assessment;
- Assessment of any new or unresolved AEs/intercurrent illnesses; and
- Urine or serum pregnancy test (for participants who were born female). Persons who are NOT of reproductive potential due to having undergone total hysterectomy or bilateral oophorectomy (verified by medical records), are not required to undergo pregnancy testing.
- Optional mucosal specimen collection
- Clinical laboratory tests for study participants who agree to provide (semen, rectal, or cervicovaginal) mucosal secretion samples, including:
  - Syphilis
  - Gonorrhea and chlamydia
  - Trichomonas vaginalis (for participants providing cervicovaginal samples),
  - Bacterial vaginosis (for participants providing cervicovaginal samples),
  - Yeast (for participants providing cervicovaginal samples, if clinically indicated).

Following completion of all procedures in the preceding list, and if results indicate that vaccination may proceed, vaccination is prepared and administered (Sections 8.3 and 8.4).

Administration of all injections during a vaccination visit must be accomplished within 1 calendar day.

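### Axillary node reactions, a listed common risk, have no guaranteed solicited assessment between the 25-60 minute check and the end of day 3

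*Combined protocol and SAP*

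**What the plan says.** Table 4-6 puts "Axillary lymph node swelling, pain, or tenderness" among the common risks. Section 4.8.1.1 includes "axillary lymphadenopathy or axillary tenderness" among the vaccination-related events of the earlier MVA/HIV62B trials.

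Section 9.10 defines the content of the reactogenicity record: "Reactogenicity assessments include assessments of systemic and local symptoms, vaccine-related lesions, and lymph nodes". Section 5.1 makes the frequency and severity of reactogenicity, by boost regimen, part of primary endpoint 1.

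Section 9.10.3 then restricts the node component: "This assessment is required only when reactogenicity assessments are performed by HVTN CRS staff, not by the participant". Table 9-1 assigns the pre-injection check and one post-injection check ("Early: 25-60 minutes after vaccination") to site staff. The remaining day 0 check and those on days 1, 2 and 3 are assigned to "HVTN CRS staff or participant".

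On visits, Section 9.10 states: "In general, a participant who self-reports any postvaccination reaction greater than mild is seen by a clinician within 48 hours after onset". It makes an exception for reactions that are improving or have resolved. Appendix G schedules no clinic visit between day 0 and day 7, or between day 112 and day 119.

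**The concern.** The protocol names a reaction as common, makes nodes part of reactogenicity, and then guarantees only one solicited look after each injection, within about an hour. If a node reaction appears later on day 0 or on days 1 to 3, nothing in the text ensures that anyone asks about it or examines for it. The axilla is not named among the systemic and local symptoms in Section 9.10.1.

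Three features of this trial give that some weight:

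- MVA/HIV62B and AIDSVAX B/E have not been given together in humans before (Sections 4.8 and 4.8.4), so reactogenicity by regimen is a main safety output.
- The two products go into opposite arms (Table 3-1), and only nodes on the injected side are assessed. The side of a node reaction therefore helps to link it to a product, and that information is lost when nodes are not assessed.
- Section 6.4.3.1 tabulates each sign at its maximum severity over all injection visits, but does not say how participants or days without a node assessment enter the percentage. A participant never examined after the first hour could be counted as having no node reaction.

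**Working it through.** **Who must do each check (Table 9-1), read with Section 9.10.3**

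| Check after injection | Performed by | Node assessment required? |
|---|---|---|
| Day 0, 25-60 minutes | Staff | Yes |
| Day 0, later | Staff or participant | Only if staff do it |
| Day 1 | Staff or participant | Only if staff do it |
| Day 2 | Staff or participant | Only if staff do it |
| Day 3 | Staff or participant | Only if staff do it |

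A required node check is certain at 1 of 5 post-vaccination checks and not certain at 4 of 5 (4/5 = 80%). Over two vaccinations, that is 8 of 10 not certain.

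**Other routes by which a node reaction could be recorded**

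- Staff may do the later checks at the site's choice, with no reaction needed to trigger them. The node assessment then applies.
- A self-reported reaction greater than mild generally leads to a clinician visit. An axillary complaint of that severity qualifies by itself.
- Participants contact the site daily and are told to report events before the next visit (Sections 9.3 and 9.10). Events not listed on a reactogenicity CRF go to the adverse experience log.
- Adverse events are assessed at every follow-up visit (Section 9.4), including days 7, 14, 119 and 126. The abbreviated examination at such visits is "a symptom-directed evaluation by history and/or appropriate physical exam based on participant self-reported symptoms or complaints" (worded so in Section 9.3, and likewise in 9.4), so it looks at the axilla only if the participant complains.

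None of these is a systematic question or examination of every participant on days 1 to 3. What they are least likely to capture is a mild or short-lived node reaction that the participant does not volunteer.

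**What incomplete capture would do to the plan's own safety figures**

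Section 6.1.1 gives the true rate with a 90% chance of at least one event as 10.9% for n = 20 and 5.6% for n = 40. Both reproduce from 1 - 0.1^(1/n): 10.87% and 5.59%.

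Let s be the fraction of participants with a node reaction in whom it is recorded. The chance of recording at least one is 1 - (1 - s × p)^n, so the true rate p needed for 90% is [1 - 0.1^(1/n)]/s. The documents do not give s, so a range is shown as an assumption.

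| Assumed s | p needed, n = 20 | p needed, n = 40 | Chance of at least one recorded if p = 10%, n = 20 |
|---|---|---|---|
| 1 | 10.9% | 5.6% | 87.8% (as in Table 6-1) |
| 0.75 | 14.5% | 7.5% | 79.0% |
| 0.5 | 21.7% | 11.2% | 64.2% |
| 0.25 | 43.5% | 22.4% | 39.7% |

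The recorded frequency has expectation s × p, so a group's percentage falls in direct proportion to s.

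**The case against.** The best defence is that the protocol has several ways to learn of a node reaction. Staff may do the day 1 to 3 checks, a moderate axillary complaint can itself bring the participant in, contact is daily, and adverse events are asked about at each later visit. A node event that reaches the adverse experience log still counts in primary endpoint 1, because Section 5.1 includes adverse event frequency. The earlier axillary events in Section 4.8.1.1 are themselves listed among adverse events, so that route has worked before. Section 9.10.3 also calls for judging enlargement and measuring the node, which it is sensible to reserve for staff.

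All of this stands, and it rules out saying that nodes go unassessed on days 1 to 3 unless some other reaction brings the participant in. It does not close the gap. Volunteered reports are not equivalent to asking every participant about a reaction that the protocol itself treats as reactogenicity.

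Two limits on the evidence also stand. The post-vaccination symptom log and the CRFs are not in the documents, so the log may already ask about the axilla; Section 9.10.1 only shows that the protocol does not say so. And the documents give no onset times for node reactions, so that 25-60 minutes is too early is plausible rather than documented.

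**Conclusion.** The gap is real but narrow. From later on day 0 to day 3, a solicited node assessment is possible but not guaranteed. Mild or transient node reactions may therefore be under-counted, or counted unevenly according to how each site conducts the checks. The size is unknown. The table under the check shows its effect for assumed capture fractions from 0.25 to 1 and is not an estimate.

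A reader might infer more: that the more reactogenic regimens will be examined more often and so show a spurious excess of node reactions. The documents allow this but do not show it. Site staff and participants are blinded (Section 6.3), and every arm receives two injections per visit. The tempting figures are the HVTN 097 local symptoms in Section 4.8.2, moderate in 28% and severe in 9%, together 37%. They do not support a calculation: they come from a different poxvirus vector, cover the whole regimen rather than one vaccination, and leave out systemic reactions, which can also prompt a visit. No matching rate is given for either product alone in this schedule, and Section 4.8.1 says MVA/HIV62B was itself followed by mild or moderate local reactions in most recipients.

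This is a low-cost improvement to data collection for a primary safety endpoint. It is not a flaw that undermines the trial.

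**What to change.** 1. In Sections 9.10.1 and 9.10.3, and in the post-vaccination symptom log if it does not already have them, add participant-reported axillary pain/tenderness and axillary swelling, left and right separately, at daily maximum severity, from day 0 to day 3.
2. Keep palpation and measurement of nodes as a staff assessment.
3. In Section 6.4.3.1, tabulate the self-reported items separately from staff-measured nodes. Use the number of participants actually assessed as the denominator for each, so that a participant not assessed is not counted as free of a reaction.
4. Leave day 7 and day 119 findings out of the reactogenicity tables. Section 9.10 sends onsets after the three-day period to the adverse experience log, and mixing the two windows would blur both.

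The cost is a few lines on the log and CRF and a denominator rule in the analysis; no visit or blood draw is added. The downside is that some mild, non-specific axillary tenderness will be recorded that would otherwise go unreported, and self-reported swelling is less reliable than palpation. That is the reason for separate tables.
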